6.2 Treatment Continuation Decisions Based on Efficacy

The decision to continue study treatment will be based on iRECIST guidelines ³⁸. Treatment will be discontinued if progressive disease is confirmed (iCPD) within 4 to 6 weeks of immune unconfirmed progressive disease (iUPD) or if iUPD is associated with clinical instability, (eg, worsening of performance status, need for increased palliative intervention or more intensive management of disease-related symptoms).

6.3 Dose Modification

6.3.1 Dose Modification and Toxicity Management for Immune-related TEAEs

Treatment-emergent AEs (TEAEs) associated with pembrolizumab exposure may represent an immunologic aetiology. These irAEs may occur shortly after the first dose or several months after

the last dose of pembrolizumab treatment and may affect more than 1 body system simultaneously. Therefore, early recognition and initiation of treatment is critical to reduce complications. Based on existing clinical study data, most irAEs were reversible and could be managed with interruptions of pembrolizumab, administration of corticosteroids and/or other supportive care. The role of BO-112 in inducing or potentiating the occurrence of anti-PD1 associated irAEs is currently unknown and therefore BO-112 treatment must also be interrupted in case of any irAE. For suspected irAEs, ensure adequate evaluation to confirm etiology or exclude other causes. Additional procedures or tests such as bronchoscopy, endoscopy, and skin biopsy may be included as part of the evaluation. Based on the severity of irAEs, withhold or permanently discontinue pembrolizumab and BO-112, and administer corticosteroids. Dose modification and toxicity management guidelines for irAEs associated with pembrolizumab and/or BO-112 are provided in [Table 5](#).

Individual subject decisions may be discussed with the Sponsor in case of a clinically stable patient or one who has clinical benefit which needs to be balanced against the potential risk of continued or re-instated study treatment (also see below for additional special cases).

Table 5 Dose modification and toxicity management guidelines for irAEs associated with pembrolizumab

General instructions:				
	1. Severe and life-threatening irAEs should be treated with IV corticosteroids followed by oral steroids. Other immunosuppressive treatment should begin if the irAEs are not controlled by corticosteroids.			
Pneumonitis	2. Anti-PD1 must be permanently discontinued if the irAE does not resolve or the corticosteroid dose is not ≤ 10 mg/day within 12 weeks of the last anti-PD1 treatment.			
	3. The corticosteroid taper should begin when the irAE is \leq Grade 1 and continue at least 4 weeks.			
	4. If anti-PD1 has been withheld, anti-PD1 may resume after the irAE decreased to \leq Grade 1 after corticosteroid taper.			
irAEs	Toxicity grade (CTCAE V5.0)	Action with anti-PD1	Corticosteroid and/or other therapies	Monitoring and follow-up
Pneumonitis	Grade 2	Withhold	Administer corticosteroids (initial dose of 1 - 2 mg/kg prednisone or equivalent) followed by taper	Monitor subjects for signs and symptoms of pneumonitis
	Recurrent Grade 2, Grade 3 or 4	Permanently discontinue	Add prophylactic antibiotics for opportunistic infections	Evaluate participants with suspected pneumonitis with radiographic imaging and initiate corticosteroid treatment
Diarrhoea / Colitis	Grade 2 or 3	Withhold		

	Recurrent Grade 3 or Grade 4	Permanently discontinue	Administer corticosteroids (initial dose of 1 - 2 mg/kg prednisone or equivalent) followed by taper	Monitor subjects for signs and symptoms of enterocolitis (ie, diarrhoea, abdominal pain, blood or mucus in stool with or without fever) and of bowel perforation (ie, peritoneal signs and ileus) Participants with \geq Grade 2 diarrhoea suspecting colitis should consider GI consultation and performing endoscopy to rule out colitis Participants with diarrhoea/colitis should be advised to drink liberal quantities of clear fluids. If sufficient oral fluid intake is not feasible, fluid and electrolytes should be substituted via IV infusion
AST or ALT elevation or Increased Bilirubin	Grade 2 ^a	Withhold	Administer corticosteroids (initial dose of 0.5 - 1 mg/kg prednisone or equivalent) followed by taper	Monitor with liver function tests (consider weekly or more frequently until liver enzyme value returned to baseline or is stable)
	Grade 3 ^b or 4 ^c	Permanently discontinue	Administer corticosteroids (initial dose of 1 - 2 mg/kg prednisone or equivalent) followed by taper	
Type 1 diabetes mellitus (T1DM) or Hyperglycemia	New onset T1DM or Grade 3 or 4 hyperglycemia associated with evidence of β -cell failure	Withhold ^d	Initiate insulin replacement therapy for subjects with T1DM Administer anti-hyperglycemic in participants with hyperglycemia	Monitor subjects for hyperglycemia or other signs and symptoms of diabetes
Hypophysitis	Grade 2	Withhold		

	Grade 3 or 4	Withhold or permanently discontinue ^d	Administer corticosteroids and initiate hormonal replacements as clinically indicated	Monitor for signs and symptoms of hypophysitis (including hypopituitarism and adrenal insufficiency)
Hyperthyroidism	Grade 2	Continue	Treat with non-selective beta-blockers (eg, propranolol) or thionamides as appropriate	Monitor for signs and symptoms of thyroid disorders
	Grade 3 or 4	Withhold or permanently discontinue ^d		
Hypothyroidism	Grade 2, 3, 4	Continue	Initiate thyroid replacement hormones (eg, levothyroxine or liothyronine) per standard of care	Monitor for signs and symptoms of thyroid disorders
Nephritis: grading according to increased creatinine or acute kidney injury	Grade 2	Withhold	Administer corticosteroids (prednisone 1 – 2 mg/kg or equivalent) followed by taper	Monitor changes of renal function
	Grade 3 or 4	Permanently discontinue		
Myocarditis	Grade 1 or 2	Withhold	Based on severity of AE administer corticosteroids	Ensure adequate evaluation to confirm aetiology and/or exclude other causes
	Grade 3 or 4	Permanently discontinue		
All Other immune-related AEs	Persistent Grade 2	Withhold	Based on severity of AE administer corticosteroids	Ensure adequate evaluation to confirm aetiology or exclude other causes
	Grade 3	Withhold or discontinue based on the event ^e		
	Recurrent Grade 3 or Grade 4	Permanently discontinue		

a AST/ALT: >3.0 - 5.0 x ULN if baseline normal; >3.0 - 5.0 x baseline, if baseline abnormal; bilirubin: >1.5 - 3.0 x ULN if baseline normal; >1.5 - 3.0 x baseline if baseline abnormal

b AST/ALT: > 5.0 to 20.0 x ULN, if baseline normal; >5.0 - 20.0 x baseline, if baseline abnormal; bilirubin: >3.0 - 10.0 x ULN if baseline normal; > 3.0 - 10.0 x baseline if baseline abnormal

c AST/ALT: > 20.0 x ULN, if baseline normal; >20.0 x baseline, if baseline abnormal; bilirubin: > 10.0 x ULN if baseline normal; >10.0 x baseline if baseline abnormal

d The decision to withhold or permanently discontinue anti-PD1 is at the discretion of the investigator or treating physician. If control achieved or ≤ Grade 2, anti-PD1 may be resumed.

e Events that require discontinuation include but are not limited to: Guillain-Barre Syndrome, encephalitis, Stevens-Johnson Syndrome and toxic epidermal necrolysis.

6.3.2 **Temporary Discontinuation/Interruption**

BO-112: IT administration may be interrupted independently of pembrolizumab treatment (which continues as scheduled), in the following situations:

- Previously injected lesion(s) has decreased to a size for which it is not feasible to administer either the full dose, or to divide the full dose across the previously injected lesion and another amenable liver lesion,
- Or the lesion(s) has become non-injectable for other reasons such as density.

Intratumoural administration of BO-112 should be resumed as soon as feasible at subsequent scheduled administrations if the lesions(s) becomes amenable (even if this may be interpreted as a sign of progression) and there is no confirmed disease progression. There is no limit on the number of such interruptions as long as there is no confirmed disease progression. However, the case should be discussed with the Sponsor if 2 or more consecutive BO-112 administrations are omitted. Pembrolizumab treatment should continue as scheduled.

Both BO-112 and pembrolizumab may be interrupted in a subject who is clinically stable and has no confirmed disease progression for situations other than those specified in the preceding paragraphs. This may include delayed toxicity/diminishing tolerability over time, medical/surgical interventions or logistical reasons not related to study treatment. These interruptions should not exceed 2 cycles unless discussed with the Sponsor. Subjects should be placed back on study treatment within 3 weeks of the scheduled interruption, unless otherwise discussed with the Sponsor. The reason for interruption should be documented in the subject's medical and study record.

6.4 **Preparation/Handling/Storage/Accountability**

BO-112:

BO-112 drug product is a sterile isosmotic suspension for IT administration, presented in a 12 mL glass vial containing 0.6 mg/mL on dry basis of active ingredient (Poly I:C) with 5% (w/v) anhydrous glucose and nominal 5.849 mM of PEI, as excipients. It is a clear to opalescent liquid, with a colourless to pale milky aspect and may contain functional visible particles. The clear glass vials (20R size) are sealed using 20 mm grey bromobutyl stoppers and aluminium caps.

BO-112 must be stored in the original carton at 2°C to 8°C and protected from light. Before being administered, vials should be gently mixed a couple of times using a sideways motion for homogenisation (avoid stirring, upside down mixing or vigorous mixing). BO-112 must be filtered prior to administration (within a time window of 2 hours). The type of filter to be used is a sterile and ready-to-use surfactant-free cellulose acetate (polyvinyl chloride-free) filter with 0.8 µm of pore size, 28 mm of diameter and 6.2 cm² of filtration area. The filter should have a bidirectional use and should be provided in a single blister pack.

Current shelf-life is 21 months. This will be updated as stability data accrue.

Pembrolizumab:

Pembrolizumab is a solution for IV infusion, presented in a 10 mL clear glass vial containing 4 mL of liquid (100 mg drug product). It is a clear to slightly opalescent, colourless to slightly yellow solution.

Pembrolizumab must be stored in the original carton at 2°C to 8°C to protect from light. Do not freeze and do not shake the vials.

After preparation of infusion: from a microbiological point of view, the product, once diluted, should be used immediately. The diluted solution must not be frozen. If not used immediately, chemical and physical in-use stability of pembrolizumab has been demonstrated for 24 hours at 2°C to 8°C. This 24-hour hold may include up to 6 hours at room temperature (at or below 25°C). If refrigerated, the vials and/or IV bags must be allowed to come to room temperature prior to use.

Accountability:

1. The investigator or designee must confirm appropriate temperature conditions have been maintained during transit for all study treatment received and any discrepancies are reported and resolved before use of the study treatment.
2. Only subjects enroled in the study may receive study treatment and only authorised study center staff may supply or administer study treatment. All study treatments must be stored in a secure, environmentally controlled, and monitored (manual or automated) area in accordance with the labelled storage conditions with access limited to the investigator and authorised study center staff.
3. The investigator, institution, or the head of the medical institution (where applicable) is responsible for study treatment accountability, reconciliation, and record maintenance (ie, receipt, reconciliation, and final disposition records).
4. Further guidance and information for the final disposition of unused study treatment are provided in the study Pharmacy Manual.

The investigator, a member of the study center staff, or a hospital pharmacist must maintain an adequate record of the receipt and distribution of all study drugs using the Drug Accountability Form. These forms must be available for inspection at any time.

6.5 Measures to Minimise Bias: Randomisation and Blinding

Not applicable as this is an open-label study.

6.6 Study Treatment Compliance

The prescribed dosage, timing and mode of administration may not be changed, except as defined in Section 1.1. Any departures from the intended regimen must be recorded in the electronic case report forms (eCRFs).

6.7 Concomitant Therapy

Any medication or vaccine (including over-the-counter or prescription medicines, vitamins, and/or herbal supplements) that the subject is receiving at the time of enrolment (within 28 days before the time of enrolment) or receives during the study must be recorded on the eCRF along with:

- Reason for use
- Dates of administration including start and end dates
- Dosage information including dose and frequency

The Medical Monitor should be contacted if there are any questions regarding concomitant or prior therapy.

A list of excluded medications/therapy is provided in [Appendix 5](#).

6.8 Treatment after the End of the Study

The Sponsor will not provide any additional care to subjects after they leave the study because such care should not differ from what is normally expected for subjects with CRC or GC/GEJ.

7.0 DISCONTINUATION OF STUDY TREATMENT AND SUBJECT DISCONTINUATION/WITHDRAWAL

7.1 Discontinuation of Study Treatment

7.1.1 Permanent Discontinuation

BO-112 should be permanently discontinued when a subject meets 1 of the conditions below or if the investigator believes that it is in best interest of the subject:

- Grade 3 AST/ALT elevation which does not resolve to Grade 2 or less within 1 week of onset
- Grade 4 AST/ALT increase
- Grade 3 or 4 increased total bilirubin
- Clinically significant hepatic bleeding/haematoma in or around injected lesion in the liver.

Note: Pembrolizumab must also be permanently discontinued in the above situations (see also [Table 5](#)**Error! Reference source not found.**), except for hepatic bleeding/haematoma in or a round injected lesion, where pembrolizumab may be continued as long as the subject is clinically stable and there is no confirmed disease progression.

Individual subject decisions regarding the above may be discussed with the Sponsor in case of a clinically stable patient or one who has clinical benefit which needs to be balanced against the potential risk of continued or re-instated study treatment.

BO-112 must be permanently discontinued when a subject meets 1 of the conditions below or if the investigator believes that it is in best interest of the subject:

- Pregnancy: See [Appendix 6](#) and Section 8.3.5
- Lost to follow-up
- Inadvertent enrolment.

If a subject who does not meet enrolment criteria is inadvertently enrolled, that subject must be discontinued from study treatment and the Sponsor or Sponsor designee must be contacted. An exception may be granted in rare circumstances for which there is a compelling safety reason to allow the subject to continue. In these rare cases, the investigator must obtain documented approval from the Sponsor or Sponsor designee to allow the subject to continue in the study. Subjects who discontinue study treatment will not be replaced.

See the SoA ([Table 1](#)) for data to be collected at the time of treatment discontinuation and follow-up and for any further evaluations that need to be completed.

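### For a Grade 3 AST/ALT rise that settles within a week and is handled as immune-related, Section 7.1.1 sets no permanent-stop trigger while Table 5 requires permanent discontinuation

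*Combined protocol and SAP*

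**What the plan says.** Section 7.1.1 opens its list with "BO-112 should be permanently discontinued when a subject meets 1 of the conditions below". The first condition is "Grade 3 AST/ALT elevation which does not resolve to Grade 2 or less within 1 week of onset". The other liver laboratory conditions, Grade 4 AST/ALT and Grade 3 or 4 total bilirubin, carry no time element. A note below the list adds that "Pembrolizumab must also be permanently discontinued in the above situations", points to Table 5, and makes one exception, for hepatic bleeding or haematoma.

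Table 5, in Section 6.3.1, is titled as guidance for immune-related events associated with pembrolizumab, and its action column is headed for anti-PD1. The row "AST or ALT elevation or Increased Bilirubin" assigns permanent discontinuation to Grades 3 and 4. The footnote that defines Grade 3 uses level alone: "AST/ALT: > 5.0 to 20.0 x ULN, if baseline normal; >5.0 - 20.0 x baseline, if baseline abnormal".

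The text of Section 6.3.1 before the table brings in BO-112. It says that the role of BO-112 in such events is unknown, "therefore BO-112 treatment must also be interrupted in case of any irAE". It then says that both drugs are to be withheld or permanently discontinued according to severity, and presents Table 5 as covering immune-related events of either drug.

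The footnote to Table 10 in Appendix 3 sends the reader to Section 7.1, not to Table 5, for the liver stopping criteria.

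**The concern.** Section 7.1.1 applies a one-week resolution condition to Grade 3 AST/ALT for both drugs and then cites Table 5 as if the two matched. Table 5 has no such condition. A site that starts from Section 7.1.1, as Appendix 3 directs, finds no permanent-stop trigger for a short-lived Grade 3 rise. A site that treats the same event as immune-related and starts from Table 5 finds that treatment must stop for good.

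This is an inconsistency in a safety stopping rule, in a trial where every subject has a liver metastasis injected and receives an anti-PD1 agent, at about 15 centres. If centres take different defaults, subjects with the same event are managed differently. The secondary tolerability measure, the number of study discontinuations due to related TEAEs, would then partly reflect which section a centre read. So would the tabulation in Section 9.3.2 of TEAEs leading to discontinuation of study treatment.

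**Working it through.** No figure in the plan needs to be reproduced and no arithmetic applies. The check sets the two rules side by side for a liver event handled as immune-related, with no other stopping condition met.

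| Event | Section 7.1.1 | Table 5 with Section 6.3.1 | Agree? |
|---|---|---|---|
| Grade 3 AST/ALT, down to Grade 2 or lower inside a week | No permanent-stop trigger | Permanent discontinuation | No |
| Grade 3 AST/ALT, not settled after a week | Permanent discontinuation | Permanent discontinuation | Yes |
| Grade 4 AST/ALT | Permanent discontinuation | Permanent discontinuation | Yes |
| Grade 3 or 4 bilirubin | Permanent discontinuation | Permanent discontinuation | Yes |

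The disagreement is confined to the first row.

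**By drug.** For pembrolizumab the conflict is direct: the note in Section 7.1.1 carries the one-week condition over to it, and the action column of Table 5 is about anti-PD1. For BO-112 the conflict comes through Section 6.3.1. The sentence that requires interruption of BO-112 would not be enough, because an interruption is not a permanent stop. The conflict rests on the later statement that both drugs are withheld or permanently discontinued by severity, and on the description of Table 5 as covering events of either drug.

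**By cause.** Section 7.1.1 sets no cause, so it covers immune-related and other elevations alike. Table 5 covers immune-related events only. A short-lived Grade 3 rise judged to have another cause, such as the injection itself, falls only under Section 7.1.1, and there is no conflict.

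**Whether the time condition can be ignored.** Within the Section 7.1.1 list only Grade 3 AST/ALT has a resolution window; the Grade 4 and bilirubin conditions have none. If Table 5 always overrode it, the window would have no effect for any immune-related event, although Section 7.1.1 does not limit it to other causes.

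**Which text governs.** Section 7.1.1 refers to Table 5, and Appendix 3 refers to Section 7.1. None of these places says which prevails when they differ.

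**Endpoints.** The primary safety endpoint counts subjects with related TEAEs of Grade 3 or higher. A related Grade 3 rise enters that count whichever stopping rule is followed. The measures that can move are those based on discontinuation.

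**The case against.** The best defence is that the two passages have different scopes. Table 5 is for immune-related events and anti-PD1; the Section 7.1.1 list is written for BO-112 and names no cause. Section 6.3.1 also tells investigators to evaluate suspected immune-related events and exclude other causes, so cause is meant to decide whether Table 5 applies. This stands as a limit on the point, which is why the point is restricted to events handled as immune-related. It does not remove the conflict, because Section 7.1.1 covers those events too and extends its conditions to pembrolizumab.

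A second defence is that the lists are cumulative. Section 7.1.1 gives sufficient reasons to stop and never says that treatment continues after a resolved Grade 3 rise, so the reference to Table 5 could mean that Table 5 applies as well. That reading is possible, but it leaves the one-week condition idle for immune-related events, and the text does not state it.

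Third, both sections let individual decisions be discussed with the Sponsor for clinically stable or benefiting subjects. That softens the consequences without saying which default the discussion starts from.

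A reader might infer more than the documents support:

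- *That sites would act in opposite ways.* Section 7.1.1 omits a trigger; it does not require continuation, and it leaves room for investigator judgement.
- *That investigators cannot separate an injection effect from an immune event within a week.* The documents do not say so. They ask for an evaluation of cause, though without a liver-specific procedure.
- *A count of affected subjects.* Any rate would be invented. The Phase I summary in Section 2.2.2 has three subjects with liver injections. Transaminases and bilirubin stayed normal in the two from Part 1, and the summary of related events lists no hepatic event. That is too little to support or exclude a rate.
- *An effect on the response endpoint.* Nothing in the documents shows one.

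**Conclusion.** The protocol is inconsistent as written on one defined event: a Grade 3 AST/ALT elevation that falls to Grade 2 or lower within a week and is handled as immune-related. Section 7.1.1 gives no permanent-discontinuation trigger for either drug. Table 5 requires permanent discontinuation of anti-PD1, and Section 6.3.1 extends the immune-related actions to BO-112.

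The conclusion rests on the wording alone, and on reading Section 6.3.1 as carrying the permanent-stop action to BO-112; for pembrolizumab that reading is not needed. Its size cannot be put as a number of subjects because no event rate is given. Its reach is patient safety and the discontinuation-based tolerability measures; the primary safety count is unaffected. The point does not extend to the other liver criteria, which agree, or to events judged not immune-related. It is worth correcting because it concerns a safety stopping rule and the correction is cheap.

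**What to change.** Reconcile Section 7.1.1, Section 6.3.1, Table 5 and the pointer in Appendix 3 so that each drug has one stated rule for Grade 3 AST/ALT. Say explicitly whether the rule depends on an immune-related cause. Make the cross-references lead to that single rule. Which rule is clinically right is for the sponsor to decide; none is proposed here.

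The cost is protocol wording. Sample size, assessment schedule and planned analyses do not change.
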